2.2. Sample Size Considerations

It was estimated approximately 800 patients (67% of the total of planned 1200 patients who would be randomized to the pivotal phase 3 studies (MVT-601-3101 or MVT-601-3102) and had completed either study) were eligible and willing to participate in this extension study.

3. PLANNED ANALYSES

The final analysis of the data includes data through Week 104 and all post-treatment follow-up data.

3.1. Final Analyses

The final analyses of all efficacy and safety data from MVT-601-3103 will occur after all enrolled patients have either completed 80 weeks of open-label treatment with relugolix + E2/NETA and the 30-day safety Follow-Up visit or discontinued early from the study. The results of the final analyses will be used for the final CSR for MVT-601-3103.

3.2. Safety Follow-Up Analyses

If the first menstruation after the end of study treatment administration is observed before the Follow-Up visit, the date of onset of the first menstruation is recorded in the eCRF. Patients whose menses has not resumed as of the Follow-Up visit for whom there is no explanation for the lack of resumption (eg, medical procedure or medications) will be contacted by telephone 3 months (+ 0.5 months) after the Follow-Up visit to determine if menses has resumed and will be asked about factors that may affect resumption of menses. If a patient is lost to follow-up, three documented attempts should be made to contact the patient by telephone. If unable to contact the patient by telephone, a certified letter must be sent to the patient.

Bone mineral density by DXA at 6-month and 12-month Post-Treatment will be proceed according to the rules mentioned in Section 2.1 Table 2. The follow-up bone densitometry will be submitted for central reading.

Post-treatment medical and gynecological history, concomitant medications, and bone fracture events will be measured at the 6-month and 12-month PTFU visits. Patients with PTFU scan bone loss $\geq 3\%$ at the lumbar spine and/or total hip compared with the pivotal study baseline will have the following clinical laboratory evaluations: vitamin D, thyroid-stimulating hormone, parathyroid hormone, creatinine, calcium, and phosphorous.

Data collected during the additional safety Follow-Up period that are available at the time of database lock for final analyses will be summarized and reported in the final clinical study report.

4. GENERAL CONSIDERATIONS FOR DATA ANALYSES AND HANDLING OF MISSING DATA

4.1. Data Presentation Conventions

All statistical analyses will be conducted using SAS[®] Version 9.2 or higher. Only descriptive analyses will be provided. Formal statistical comparisons are not planned.

All confidence intervals (Cis) will be reported as two-sided 95% Cis unless otherwise stated.

Where appropriate, variables will be summarized descriptively by study visit. For the categorical variables, the count and proportions of each possible value will be tabulated by pivotal phase 3 study treatment group. For continuous variables, the number of patients with non-missing values, mean, median, standard deviation (SD), minimum, and maximum values will be tabulated.

Unless otherwise specified, the following conventions will be applied to all analyses:

- Mean and median values will be formatted to one decimal place, unless otherwise specified. For BMD DXA, mean and median values will be formatted to two decimal places. Standard deviation values will be formatted to two more decimal places, unless otherwise specified. Minimum and maximum values will be presented to the same number of decimal places as the measured value. If the measured value is large (eg, > 100), fewer decimal places may be displayed.
- Percentages will be rounded to one decimal place.
- P values will be rounded to four decimal places. P values < 0.0001 will be presented as "< 0.0001" and p values > 0.9999 will be presented as "> 0.9999".
- 1 month = 30.4375 days. Month is calculated as (days/30.4375) rounded to one decimal place.
- 1 year = 365.25 days. Year is calculated as (days/365.25) rounded to one decimal place.
- Age will be calculated using the date of randomization in pivotal phase 3 study. If only year of birth is collected, 1 July of the year of birth will be used to calculate age.
- 1 pound = 0.454 kg.
- 1 inch = 2.54 cm.
- Missing efficacy or safety data will not be imputed, unless otherwise specified.
- For laboratory results above or below sensitivity limits displayed as "<" or ">" a quantification threshold, 0.000000001 will be subtracted or added, respectively, to the threshold to derive a numeric result for analysis.
- For safety analyses, percentages will be calculated based on the number of patients in the analysis population in each pivotal phase 3 study treatment group.

- For by-visit observed data analyses, percentages will be calculated based on the number of patients with non-missing data as the denominator, unless otherwise specified;
- For other continuous endpoints, the summary statistics will include mean, SD, median, minimum, and maximum.
- For time-to-event endpoints, the summary statistics will include median time to event-free survival, the 25th and 75th percentiles, and the number of patients at risk at specified time points.
- For categorical endpoints, the summary statistics will include counts and percentages;
- Confidence intervals will be constructed at the 95% level. For binomial variables, exact methods will be employed, unless otherwise specified.

4.2. Analysis Populations

The protocol specified efficacy and safety analyses will be performed on the Extension Study Population as defined in Section 4.2.1 and Section 4.2.2, respectively. The Week 52 efficacy analyses will include efficacy data up to 52 weeks of treatment on the Extension Study population. The Week 52 safety analyses will include safety data up to 52 weeks or safety Follow-Up if patients early terminated the study before Week 52 on the Extension Safety population. The final analysis will include efficacy data up to 104 weeks of treatment on the Extension Study Population and safety data up to safety Follow-Up on the Extension Safety population.

4.2.1. Extension Study Population

The Extension Study population is defined as all patients who enrolled into MVT-601-3103 and who have received any amount of open-label study drug in MVT-601-3103. All efficacy analyses will be performed on the Extension Study population, unless otherwise specified. Efficacy analyses will be performed by treatment group as randomized in the pivotal phase 3 study.

4.2.2. Extension Safety Population

The Extension Safety population is defined as all enrolled patients who received any amount of open-label study drug in MVT-601-3103. Any patient who received at least one dose of relugolix will be considered as a relugolix patient for purposes of safety analyses, consistent with analysis in the pivotal phase 3 studies. All safety analyses will be performed on the Extension Safety population, unless otherwise specified. Safety data will be analyzed by pivotal phase 3 study treatment group according to the actual treatment received (not the randomized treatment) in pivotal phase 3 study.

4.2.3. Exclusion of Site PPD from Efficacy and Safety Analyses

Due to the results of an audit which found evidence of data integrity issues at the Site PPD (in study MVT-601-3102), the data of three patients enrolled into the open-label extension study at that site will be excluded from all efficacy and safety analyses. The data for these three patients

will be presented in disposition table and listing, and in listing of patients excluded from efficacy and safety analyses.

4.3. Definitions, Computation, and Convention

4.3.1. Definition of Date of First Dose and Date of Last Dose of Pivotal phase 3 Study Drug

The date of first dose of pivotal phase 3 study drug is defined as the date when a patient receives the first dose of study drug (relugolix/placebo or E2/NETA/placebo) following randomization in study MVT-601-3101 or MVT-601-3102. The date of last dose of pivotal phase 3 study drug is defined as the date a patient receives the last dose of study drug in the pivotal Phase 3 study MVT-601-3101 or MVT-601-3102, prior to or on the Week 24 visit date. The exact date of last dose of pivotal phase 3 study drug will be known for all patients entering the MVT-601-3103 study.

4.3.2. Definition of Date of First Dose and Date of Last Dose of Extension Study Drug

The date of first dose of extension study drug is defined as the date when a patient receives the first dose of open-label study drug (relugolix or E2/NETA) in the MVT-601-3103 study. The date of last dose of extension study drug is defined as the date a patient receives the last dose of open-label study drug in the MVT-601-3103 study. If the complete date of last dose of extension study drug is unknown, the last date the extension study drug was dispensed will be used. For patients missing only the day of the last dose of extension study drug, either first of the month of last dose of extension drug or last date extension study drug was dispensed will be used, whichever is later.

4.3.3. Study Day

Study day will be calculated with respect to the date of the first dose of study drug in the pivotal phase 3 study (Study Day 1). For assessments conducted on or after the date of the first dose of pivotal phase 3 study drug, study day will be calculated as:

$$(\text{Assessment date} - \text{date of first dose of pivotal phase 3 study drug}) + 1$$

For assessments conducted before the date (and time) of the first dose of pivotal phase 3 study drug, study day will be calculated as:

$$(\text{Assessment date} - \text{date of first dose of pivotal phase 3 study drug})$$

4.3.4. Extension Study Day

Extension study day will be calculated with respect to the date of the first dose of open-label study drug in the extension study (Extension Study Day 1). For assessments conducted on or after the date of the first dose of extension study drug, extension study day will be calculated as:

$$(\text{Assessment date} - \text{date of first dose of extension study drug}) + 1$$

For assessments conducted before the date (and time) of the first dose of extension study drug, extension study day will be calculated as:

$$(\text{Assessment date} - \text{date of first dose of extension study drug})$$

4.3.5. Definition of Overall Treatment Duration

In the final analysis, overall treatment duration is defined as the duration of time from the date of the first dose of pivotal phase 3 study drug to the date of the last dose of extension study drug as follows:

$$(\text{Date of last dose of extension study drug} - \text{Date of first dose of pivotal phase 3 study drug}) + 1$$

For patients missing day and month of the last dose date of extension study drug, the last date extension study drug was dispensed will be used to calculate overall treatment duration. For patients missing only day for date of last dose of extension study drug, the later of first of the month of last dose of extension drug or last date extension study drug was dispensed will be used to calculate treatment duration.

4.3.6. Definition of Extension Study Treatment Duration

In final analysis, extension study treatment duration is defined as the duration of time from the date of the first dose of extension study drug to the date of the last dose of extension study drug as follows:

$$(\text{Date of last dose of extension study drug} - \text{Date of first dose of extension study drug}) + 1$$

For patients missing day and month for date of last dose of extension study drug, the last date extension study drug was dispensed will be used to calculate extension study treatment duration. For patients missing only day for date of last dose of extension study drug, the later of first of the month of last dose of extension drug or last date extension study drug was dispensed will be used to calculate treatment duration.

4.3.7. Definition of Baseline Value and Post-Baseline Value

Unless otherwise specified, Baseline values are defined as the last measurement before the first administration (date and time) of study drug in the pivotal phase 3 study. A post-Baseline value is defined as a measurement taken after the first administration of study drug in the pivotal phase 3 study. Change from Baseline is defined as (post-Baseline value – Baseline value). Both date and time of study drug administration and measurement will be considered when calculating Baseline value. If the time is not available, then the date alone will be used.

4.3.8. Visit Windows

Visit windows, which will be used to associate assessments with a scheduled visit, will be used only for summarizing data by visit. The windows for scheduled assessments are shown in [Table 3: Visit Windows for Monthly and Quarterly Assessments \(Monthly and Quarterly Visit, Lab and PGA\) \(Monthly and Quarterly Visit, Lab and PGA\)](#), [Table 4 \(BMD\)](#), [Table 5 \(electrocardiogram \[ECG\]\)](#), [Table 6 \(EHP-30\)](#), [Table 7 \(EHP work domain and EQ-5D-5L\)](#), [Table 8 \(PGIC\)](#), [Table 9 \(Endometriosis Biopsy\)](#), [Table 10 \(Mammogram\)](#), and [Table 11 \(eDairy\)](#) respectively. For safety assessments, the study day will be used to determine the associated visit window. There will be no separation of data from the pivotal phase 3 and extension study. For example, if an assessment in the extension study falls in the Week 24 visit window, it will be summarized as Week 24.

If the results from more than one assessment are within a given visit window, the non-missing result from the assessment closest to the target date will be used. If two assessments are equally close to the target day, the earlier assessment will be used. For summaries of shift from Baseline in safety parameters, all values will be considered for these analyses.

Table 3: Visit Windows for Monthly and Quarterly Assessments (Monthly and Quarterly Visit, Lab and PGA)

Visit	Start Day	Target Day	End Day
Week 4 ^a	1(2 ^b)	29	43
Week 8	44	57	71
Week 12	72	85	99
Week 16	100	113	127
Week 20	128	141	155
Week 24	156	169	183
Week 28	184	197	211
Week 32	212	225	239
Week 36	240	253	267
Week 40	268	281	295
Week 44	296	309	323
Week 48	324	337	351
Week 52	352	365	411
Week 65	412	456	502
Week 78	503	547	593
Week 91	594	638	684
Week 104	685	731	Date of last dose + 6 days
Safety Follow-Up ^c	Date of last dose + 7 days	Date of last dose + 30 days	Date of last dose + 60 days

^a Start day of Week 4 for study day 1 includes only post-Baseline assessments that occurred after the first dose.

^b For Patient Global Assessments (PGAs), the start day of the Week 4 visit window begins at Day 2.

^c The safety Follow-Up visit window will be restricted to assessments prior to the date of initiation of another investigational agent or hormonal therapy affecting the hypothalamic- pituitary- gonadal axis or surgical intervention for endometriosis-associated pain.

Table 4: Visit Windows for Bone Mineral Density Assessments

Visit	Start Day	Target Day	End Day
Week 12	64	85	106
Week 24	148	169	196
Week 36	197	253	308
Week 52	309	365	421
Week 104	647	731	815
6-month post-treatment Follow-Up	Date of last dose + 150 days	Date of last dose + 180 days	Date of last dose + 304 days
12-month post-treatment Follow-Up	Date of last dose + 305 days	Date of last dose + 365 days	Date of last dose + 425 days

Table 5: Visit Windows for ECG Assessments

Visit	Start Day	Target Day	End Day
Week 12	64	85	106
Week 24	148	169	196
Week 52	309	365	421
Week 104	675	731	787

Table 6: Visit Windows for EHP-30 Questionnaire Assessments

Visit	Start Day	Target Day	End Day
Week 12	64	85	106
Week 24	148	169	196
Week 36	197	253	308
Week 48	309	337	351
Week 52	352	365	421
Week 78	491	547	603
Week 104	675	731	787

Table 7: Visit Windows for EHP Work Domain and EQ-5D-5L Assessments

Visit	Start Day	Target Day	End Day
Week 24	128	169	196
Week 52	309	365	421
Week 78	491	547	603
Week 104	675	731	787

Table 8: Visit Windows for PGIC Assessments

Visit	Start Day	Target Day	End Day
Week 12	64	85	106
Week 24	148	169	196
Week 36	197	253	308
Week 52	309	365	421

Table 9: Visit Windows for Endometrial Biopsies Assessments

Visit	Start Day	Target Day	End Day
Week 24	128	169	196
Week 52	309	365	421
Week 104	675	731	787
Safety Follow-Up ^a	Date of last dose + 7 days	Date of last dose + 30 days	Date of last dose + 60 days

^a Assessments will be excluded from analysis if they occur on or after the date of initiation of another investigational agent or hormonal therapy affecting the hypothalamic- pituitary- gonadal axis or surgical intervention for endometriosis-associated pain. Assessments after date of last dose of extension study drug + 30 days will also be excluded from analysis.

Table 10: Visit Windows for Mammogram Assessments

Visit	Start Day	Target Day	End Day
Week 52	309	365	421
Week 104	675	731	787

For patients who are or become ≥ 40 years old during the study.

Mammogram assessments are required only by protocol amendment 3.0 and 3.1.

Table 11: Time Windows for Daily Assessments from eDiary

Visit	Target Study Day of Visit ^a	Days Included in Assessment Period Window
Week 4	X ₁	1 to X ₁
Week 8	X ₂	(X ₂ - 34) to ≤ X ₂
Week 12	X ₃	(X ₃ - 34) to ≤ X ₃
Week 16	X ₄	(X ₄ - 34) to ≤ X ₄
Week 20	X ₅	(X ₅ - 34) to ≤ X ₅
Week 24	X ₆ ^b	(X ₆ - 34) to ≤ X ₆
Week 28	X ₇	Maximum [OLE start day ^c , (X ₇ - 34)] to ≤ X ₇
Week 32	X ₈	Maximum [OLE start day ^c , (X ₈ - 34)] to ≤ X ₈
Week 36	X ₉	(X ₉ - 34) to ≤ X ₉
Week 40	X ₁₀	(X ₁₀ - 34) to ≤ X ₁₀
Week 44	X ₁₁	(X ₁₁ - 34) to ≤ X ₁₁
Week 48	X ₁₂	(X ₁₂ - 34) to ≤ X ₁₂
Week 52	X ₁₃	(X ₁₃ - 34) to ≤ X ₁₃
Week 65 ^g	X ₁₄	(X ₁₄ - 56) to ≤ X ₁₄
Week 78 ^g	X ₁₅	(X ₁₅ - 56) to ≤ X ₁₅
Week 91 ^g	X ₁₆	(X ₁₆ - 48) to ≤ X ₁₆
Week 104 ^g	X ₁₇	(X ₁₇ - 51) to ≤ X ₁₇
Week104/EOT ^c	X ₁₇	Maximum [OLE start day ^c , (X ₁₇ - 34)] to ≤ X ₁₇ or PAP ^f

Abbreviation: EOT = end of treatment, OLE = open label extension.

Error! Reference source not found. Refer to **Error! Reference source not found.** Table 3 for target study day for Weeks 4, 8, 12, 16, 20, 24, 28, 32, 36, 40, 44, 48, 52, 65, 78, 91, 104 and safety Follow-Up.

^b The target study day for Week 24 is defined as date of last dose of randomized study treatment in pivotal phase 3 study. The Week 24 assessment period is defined as the 35 days up to and including the date of last dose of randomized study treatment in pivotal phase 3 study, which should occur on the day prior to the Week 24 visit.

^c OLE start day = day of first dose administered of extension study treatment.

^e The target study day for Week 104/EOT for purposes of visit window calculations is defined as date of last dose of study treatment in the extension study.

^f If the last 35 calendar days prior to and including date of last dose of study drug are not entirely within an eDiary collection period, then days of the pain assessment period (PAP) will be determined as follows: (1) if the date of last dose occurs during the eDiary collection period, the PAP will be the last 35 days which are counted during up to two eDiary collection periods immediately prior to and including date of last dose of study drug (2) if the date of last dose occurs outside of the eDiary collection period, the PAP will be the last 35 days which are counted during up to two eDiary collection period(s) immediately prior to but not including date of last dose of study drug.

^g: For Week 65, Week 78, Week 91 and Week 104, only data collected within eDiary cycles required by protocol is included in the analysis.

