9.3.3. Endometrial Biopsy

The protocol-specified endometrial biopsy procedure was performed at Baseline for all patients in MVT-601-3101 and MVT-601-3102, and at the pivotal phase 3 study Week 24/ET visit for all patients who participated in MVT-601-3101 only. Starting from protocol amendment 2.0, endometrial biopsy procedure was required for all patients in the extension study at Week 52 and Early Termination Visit (except for patients whose last dose of study drug was taken during Week 32 or earlier or within four weeks after completion of the Week 52 endometrial biopsy). However, the procedure may have been done if it would aid in the evaluation of an ongoing adverse event. An endometrial biopsy at Week 104 was recommended for all patients who complete the open-label extension; however, patients have the option to opt out. Consensus readings by independent pathologists were performed on all endometrial biopsies.

The Week 52, Week 104, and Early Termination endometrial biopsy samples will be submitted to the central laboratory. If the Week 52, Week 104, or Early Termination biopsy specimen is inadequate, a transvaginal ultrasound for endometrial thickness should be obtained and read locally. The transvaginal ultrasound findings will be used to determine if further action is required. No further action is required for endometrial thickness ≤ 5 mm. Repeat endometrial sampling will be collected for endometrial thickness > 5 mm at any location or any other endometrial abnormality is present. Unscheduled endometrial biopsies may also be performed when medically indicated and as deemed necessary by the investigator.

Endometrial biopsies will be summarized using frequencies and percentages according to primary diagnosis and secondary diagnosis from the consensus reading (Table 23). Primary and secondary diagnosis from consensus reading evaluation are summarized Table 23. Endometrial biopsies performed in the pivotal phase 3 studies and extension study will be summarized by pivotal phase 3 study treatment group and by visit. Any repeat endometrial biopsies performed will also be summarized. Biopsy reported in the pivotal study CSRs will be excluded from the extension study analyses. All endometrial biopsy findings and transvaginal ultrasound data will also be provided in a by-patient listing, including visits in both the pivotal phase 3 study and extension study.

Table 23: Categories of Primary Diagnosis in Endometrial Biopsies

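### By-visit endometrial biopsy results are chosen by nearness to the target day, with no adequacy or severity criterion, and the denominator is not fixed, so hyperplasia and carcinoma rates can be understated

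*SAP*

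**What the plan says.** **Selection.** SAP 4.3.8 sets one rule for all windowed assessments: "the non-missing result from the assessment closest to the target date will be used". On ties, "If two assessments are equally close to the target day, the earlier assessment will be used". The only stated departure is "For summaries of shift from Baseline in safety parameters, all values will be considered for these analyses", and no biopsy shift table is planned. The rule reaches biopsies through Table 9, "Visit Windows for Endometrial Biopsies Assessments", whose Week 52 window runs from Day 309 to Day 421 with target Day 365. A footnote on the Safety Follow-Up row adds: "Assessments after date of last dose of extension study drug + 30 days will also be excluded from analysis".

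**Summary.** Section 9.3.3 states: "Endometrial biopsies will be summarized using frequencies and percentages according to primary diagnosis and secondary diagnosis from the consensus reading". This is done by pivotal treatment group and visit. Table 23 has separate rows for Inadequate and Missing. After an inadequate specimen, an ultrasound is obtained, and sampling is repeated if the endometrium is thicker than 5 mm or another abnormality is present. Unscheduled biopsies are allowed when medically indicated. Repeat biopsies are also to be summarized, and all biopsy findings are listed by patient.

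**Denominator.** Section 9.3.3 names none. Section 4.1 has two general rules. One is: "For safety analyses, percentages will be calculated based on the number of patients in the analysis population in each pivotal phase 3 study treatment group". The other bases percentages in by-visit observed-data summaries on patients with non-missing data. At Week 104, "patients have the option to opt out" of the biopsy.

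**The concern.** Endometrial histology is a rare-event safety outcome for up to two years of treatment that includes estradiol. For such an outcome the visit table should show the most informative sample available. A rule based only on calendar distance can instead show an uninformative one, although 9.3.3 itself calls for the repeat that would resolve it.

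Other safety data have a worst-case summary to offset the nearest-day choice: worst post-Baseline toxicity grade for laboratory tests (9.2) and maximum post-Baseline QTcF (9.3.1). No worst post-Baseline or any-time biopsy diagnosis is described.

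The denominator adds a second source of dilution. An inadequate specimen cannot show hyperplasia or carcinoma, yet it stays in the denominator under either general rule. Women without a sample may be in it too.

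**Working it through.** The plan states no biopsy rate, inadequate fraction or precision target, so there is no figure to reproduce. The check has two parts.

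**1. Selection in the Week 52 window (Days 309–421, target 365).** Distance = |day − 365|; the smaller distance wins and ties go to the earlier sample.

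| First biopsy | Later biopsy | Distances | Result used |
|---|---|---|---|
| Day 365, inadequate | Day 400, adequate repeat | 0 and 35 | Inadequate |
| Day 370, normal | Day 405, unscheduled, hyperplasia | 5 and 40 | Normal |
| Day 350, inadequate | Day 395, adequate repeat | 15 and 30 | Inadequate |

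A repeat always follows the sample it replaces. If the inadequate biopsy falls on or after the target day, the repeat is necessarily farther away, or tied if on the same day, and cannot be chosen. If the inadequate biopsy comes before the target, the outcome depends on timing. After Day 350 (distance 15), a repeat by Day 379 (distance 14) wins, while one on Day 380 (distance 15) ties and loses to the earlier sample.

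This rests on treating an inadequate specimen as a non-missing result. The separate rows in Table 23 support that reading, though no sentence states it.

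**2. Denominator.** Let *i* be the inadequate fraction of samples taken and *m* the fraction of women with no sample. Hold the number of cases fixed.

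- Non-missing rule: reported rate = adequate-sample rate × (1 − *i*).
- Population rule: reported rate = adequate-sample rate × (1 − *m*) × (1 − *i*).

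Neither fraction is in the SAP. Assumed ranges are *i* = 5–30% and *m* = 0–40%.

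| *m* | *i* | Non-missing rule | Population rule |
|---|---|---|---|
| 0% | 5% | 0.95 | 1.00 × 0.95 = 0.95 |
| 20% | 15% | 0.85 | 0.80 × 0.85 = 0.68 |
| 40% | 30% | 0.70 | 0.60 × 0.70 = 0.42 |

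These factors are ratios and do not depend on group size. They exclude the selection effect in part 1, which acts on the numerator and cannot be sized from the document.

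**The case against.** **Events are not lost.** The windows in 4.3.8 serve only by-visit summaries. Repeats are also summarized and every biopsy is listed, so a reader who infers that a hyperplasia case vanishes from the report goes too far. This stands. What remains is that the SAP does not say whether a repeat replaces the inadequate result, adds to it or sits apart. An unscheduled biopsy is also not clearly a repeat. If the 30-day footnote to Table 9 reaches beyond the row it marks, a late repeat after an inadequate final biopsy could be left to the listing.

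**The nearest-day rule is neutral to the finding.** It is prespecified, and a nearer hyperplasia beats a farther normal sample. This also stands, so for two adequate samples the worst-in-window choice is partly a preference. It does not answer the choice of an inadequate sample over an adequate one.

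**Missing samples are not fixed in the denominator.** One might infer from the Missing row in Table 23, with the population rule in 4.1, that women without a biopsy are counted. The plan does not settle this. The by-visit rule in 4.1 would exclude them, 4.4.1 confines by-visit endpoints to observed records, and the rule that counts missing observations in denominators (7.1.1) sits in the efficacy section. A Missing row may be only a displayed count.

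**The dilution is visible.** With Inadequate and Missing shown as rows, a reader can recompute the rate. That is true of the denominator, but not of the selection.

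**Conclusion.** The point holds as a possibility created by the wording, not as a certain bias. As written, 4.3.8 can put an inadequate biopsy in the visit table in place of an adequate repeat, and a nearer normal sample in place of an unscheduled one with hyperplasia. No worst post-Baseline biopsy summary offsets this. The by-visit rate is understated only when a more informative or more severe result lies farther from the target in the same window, or ties and comes later.

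On the denominator, the defect is an unresolved overlap between two rules in 4.1, neither of which removes inadequate samples. Under the assumed fractions the reported rate is 0.70–0.95 of the adequate-sample rate under the non-missing rule and 0.42–0.95 under the population rule. The latter is lower whenever samples are missing, which the Week 104 opt-out makes likely.

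A reader might want to express this as a rate or upper bound on the roughly 800 women planned. The documents do not support that: biopsies are summarized by pivotal treatment group and visit, and 9.3.3 asks for frequencies and percentages without a confidence interval.

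**What to change.** In 4.3.8 and 9.3.3, state for endometrial biopsies that:

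- an adequate sample supersedes an inadequate one in the same window, and Inadequate is reported only when no adequate sample exists there;
- the visit value is the worst adequate consensus diagnosis among scheduled, repeat and unscheduled biopsies in the window. Alternatively, add a worst post-Baseline diagnosis summary;
- diagnosis percentages are based on women with an adequate biopsy in the window, by pivotal treatment group, with inadequate and not-done shown as counts outside the denominator.

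Also say whether the 30-day exclusion under Table 9 applies only to the Safety Follow-Up row.

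The cost is SAP wording and one table shell. No new biopsy or reading is needed. The reported rates may be slightly less favourable, and a worst-in-window rule gives women with several biopsies more chances of an adverse diagnosis, which a table footnote should state.
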